## Sample Size Justification

Sample size was determined to have sufficient power to detect differences between study conditions corresponding to our primary hypotheses regarding point prevalence smoking abstinence at late pregnancy and 24weekpostpartum assessments, fetal growth, birth weight, and breastfeeding. Estimates of abstinence were based on our prior trials where 7-day point-prevalence abstinence in the incentives vs. control conditions were 34% vs. 7% at the late-pregnancy assessment and 14% vs. 1% at 24weeks postpartum assessment, respectively (Higgins et al., 2010a). We estimated that the proposed increase in the value of the incentives used with heavier smokers will increase late-pregnancy abstinence rate to approximately 50% in the incentives condition while the best practices alone condition is estimated at <10%. Assuming a decline in abstinence of approximately 20% from late-pregnancy to the 24-week postpartum assessment as we saw in our prior trials, we estimate abstinence rates of approximately 30% vs. < 5% at 24weeks postpartum in the best practices plus incentives vs. best practices alone conditions, respectively. The proposed sample size of 115 per study condition will result in greater than 90% power to detect a difference between the two treatment conditions in abstinence rates of 50% vs. 10% at late-pregnancy or 30% vs. 5% at 24weeks postpartum assessments using a chi-square test. The proposed sample size is also expected to be more than sufficient for examining differences between study conditions in fetal growth, birth weight, and breastfeeding outcomes. The proposed sample size after considering noncompliance in completing scheduled ultrasounds is estimated to have power of 80% for detecting a mean growth difference of 23 g/wk in estimated fetal weight between any two conditions based on our estimated pooled within group SD=49.7. This difference is slightly more than half the difference observed between the incentive and control condition in our 2008 study (Heil et al, 2008) and represents a conservative expected difference. With respect to mean birth weight, power is estimated to be 80% to detect a difference of approximately 200 g between any two study conditions assuming a pooled SD=550, which aligns well with treatment effects in our study combining results across prior trials (Higgins et al., 2010a) where

mean birth weights were  $3295.6 + 588$  g vs.  $3093.6 + 603$  g in the incentives and control conditions, respectively and with our estimate of a mean birth weight of  $3595.6 + 404$  g in the nonsmoker condition. For this estimate of the mean birth weight that might be expected in the nonsmoker condition, we examined birth weights in a sample ( $n = 88$ ) of women followed in our clinic who were smokers at the time that they learned of the current pregnancy but quit prior to entering prenatal care (i.e., spontaneous quitters) and were continuously abstinent through the remainder of antepartum. We are estimating breastfeeding rates of 50% and 30% in the incentives condition and 17% and 13% in the best practices alone condition at 12 and 24 weeks postpartum, based on our prior study results (Higgins et al., 2010b) and our planned use of higher value vouchers with heavier smokers in the proposed study. Again using the same group of spontaneous quitters but restricting it to women who remained abstinent through 24-weeks postpartum ( $n=32$ ), the estimated percent breastfeeding at 12- and 24-weeks postpartum was 70% and 48%. Using chi-square tests, we will have over 80% power to detect differences in rates between any two of the three study conditions at the two assessments. Power calculations were done using a two-sided significance level of .05.

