## Project Summary

Smoking during pregnancy is the leading preventable cause of poor pregnancy outcomes in the U.S. Most pregnant smokers continue smoking through pregnancy producing serious immediate and longer-term adverse health consequences for the infant. Smoking during pregnancy is highly associated with economic disadvantage and a substantive contributor to health disparities. Efficacious interventions are available, but cessation rates are low (<15%) and improvements in birth outcomes often modest or absent. Current treatments usually entail relatively brief, low-cost interventions (e.g., pregnancy-specific quitlines). There is broad consensus that more effective interventions are sorely needed. We have developed a novel behavioral economic intervention in which women earn financial incentives contingent on smoking abstinence. In a meta-analysis of treatments for smoking during pregnancy, effect sizes achieved with financial incentives were severalfold larger than those achieved with lower intensity approaches or medications. The intervention also appears to improve birth outcomes and increase breastfeeding duration. While highly promising, further research is needed in at least three areas. (1) The evidence on birth outcomes and breastfeeding is from studies that combined data across trials rather than a single prospective trial, (2) whether the intervention produces other postpartum improvements in health has not been investigated, and (3) the overall cost effectiveness of this approach has not been examined. To examine these unanswered questions, we are proposing a randomized, controlled clinical trial comparing the efficacy and cost effectiveness through one-year postpartum of current best practices for smoking cessation during pregnancy vs. best practices plus financial incentives among 230 pregnant, Medicaid recipients. We will also include a third condition of 115 pregnant nonsmokers matched to the smokers on sociodemographic and health conditions to compare the extent to which the treatments reduce the burden of smoking and to estimate how much more might be accomplished by further improvements in this incentives intervention without exceeding cost effectiveness. We hypothesize that best practices plus financial incentives will be more effective than best practices alone, that the incentives intervention will be cost effective, and that while

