## Statistical Methods

Study conditions will be compared on baseline demographics and other characteristics using analysis of variance for continuous variables and chi-square tests for categorical variables. If a specific characteristic differs significantly across study conditions and is predictive of outcome, it will be considered as a potential covariate in subsequent analyses. Analyses of treatment effects on smoking status will be limited to smokers randomized to the two treatment conditions. We will adhere to an intent-to-treat approach (Armitage, 1983) wherein all women randomized to the study conditions will be included in the analyses independent of early dropout, noncompliance, etc., with the exception of excluding women for abortion/fetal demise as is convention in this research area. Cochran Mantel Haenszel tests (CMH) will be performed for comparisons of the two treatment conditions on point-prevalence smoking abstinence at end-of-pregnancy and 6-months postpartum assessments with

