referring clinic as a stratification variable. The Breslow-Day Test will be used to examine the homogeneity of treatment effects across referring clinics. Comparisons of point-prevalence abstinence rates between treatment conditions across all assessments through one-year postpartum will be analyzed using mixed model repeated measures for categorical data based on generalized estimating equations (GEE) utilizing a logistic link function (SAS: PROC GENMOD, SAS Institute, Cary, NC). We will include women from the nonsmoker condition in analyses of fetal growth, birth outcomes, and breastfeeding and other postpartum outcomes. Comparisons of treatment conditions on dichotomous outcomes (e.g. % low birth weight, % preterm, % NICU admissions, % breastfeeding, % medical treatment in first year) will parallel categorical analyses for point prevalence abstinence using PROC GENMOD to adjust for strata (referring clinics) and potential covariate effects. Analysis of covariance will be used to compare study conditions on mean birth weight adjusting for variables known to predict birth weight (i.e., maternal prepregnancy BMI, parity, and sex), mean gestational age at delivery, and frequency measures of medical illnesses. Statistical analyses of fetal growth outcomes (i.e. estimated fetal weight, fetal lean area, fat area, femur length and head circumference) will be based on linear growth models with slope and intercept as random effects (SAS PROC MIXED). This methodology allows for the within-subjects ultrasound assessments not to be at identical timepoints across subjects. Study condition will be considered a fixed factor with fetus nested within study condition. Two-way analyses of covariance will also be used for analyzing effects of study condition and referring clinic on DEXA body composition measures at 12 months. Additional subject level covariates will include maternal pre-pregnancy body mass index, maternal age and fetal gender. Analyses of infant growth will parallel those used to examine fetal growth. Repeated measures analyses of variance will be used to test for differences between study conditions in skinfold thickness obtained during infant 1st year of life and continuous measures of medical illnesses. Significance will be based on alpha = .05 for all analyses.

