### **Economic Evaluation**

**Cost analysis.** We will conduct an economic evaluation from the societal perspective including both cost-effectiveness and cost-benefit analyses (Drummond et al., 2005). The outcome measures in this trial were described above, with antepartum abstinence being primary and the related outcomes of longer-term abstinence, birth outcomes, and health and health care utilization in the 1st year postpartum important as well. Each of these outcomes can be viewed from the perspective of incremental cost effectiveness (e.g., the incremental cost to produce an additional abstinent mother at final antepartum assessment). We hypothesize that the best practices plus incentives intervention will be cost-effective (i.e., dominant) as compared to the best practices alone condition. To determine the cost of each intervention, we will employ the Brief Drug Abuse Treatment Cost Analysis Program (Brief DATCAP; French et al., 2004; French, 2010), which has been widely used in the area of

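### The 80% power for a 200 g birth-weight difference does not hold for the randomised comparison: with the plan's own SDs it is about 72% unadjusted

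*Combined protocol and SAP*

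**What the plan says.** The Sample Size Justification makes one birth-weight claim for all three pairwise contrasts: "power is estimated to be 80% to detect a difference of approximately 200 g between any two study conditions assuming a pooled SD=550". It says that this agrees with the group's earlier pooled results and then lists them: 3295.6 g (SD 588) with incentives and 3093.6 g (SD 603) in controls, a difference of 202 g. For nonsmokers it expects 3595.6 g (SD 404), taken from 88 women who quit before entering prenatal care. The test level is given at the end of the section: "Power calculations were done using a two-sided significance level of .05". The number per condition, 115, comes from the abstinence calculation: "The proposed sample size of 115 per study condition will result in greater than 90% power".

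The analysis is set out under Statistical Methods: "Analysis of covariance will be used to compare study conditions on mean birth weight adjusting for variables known to predict birth weight". The variables named there are maternal pre-pregnancy BMI, parity and sex. The section also says: "We will include women from the nonsmoker condition in analyses of fetal growth, birth outcomes, and breastfeeding and other postpartum outcomes". Neither section gives an expected R-squared, says how 550 was obtained, or describes it as an adjusted SD.

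**The concern.** Any pooled SD lies between the SDs that go into it. An SD of 550 is below both 588 and 603, so it cannot describe the comparison of incentives with best practices, which is the only randomised contrast. It can be approached only by bringing in the less variable nonsmoker group or by assuming a covariate adjustment that the plan does not state.

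This matters for how a null result is read. The Sample Size Justification lists birth weight among its primary hypotheses, and the Project Summary gives a gap in the birth-outcome evidence as a reason for the trial: "The evidence on birth outcomes and breastfeeding is from studies that combined data across trials rather than a single prospective trial". A non-significant birth-weight difference between the randomised arms would be judged against a 20% chance of missing 200 g, when the plan's own inputs put that chance nearer 28% unadjusted.

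**Working it through.** **Inputs.** From the Sample Size Justification: n = 115 per condition, two-sided alpha .05, difference 200 g (202 g in the prior data), stated SD 550, and group SDs of 588, 603 and 404. The R-squared values and the data-loss rates below are assumptions, because the plan gives none.

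**Method.** Two-sample t-test with 228 degrees of freedom. Noncentrality = difference / (SD × √(2/115)), critical value 1.970, power from the noncentral t distribution.

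**1. The plan's figure.** With SD 550 the standard error is 550 × √(2/115) = 72.5 g and the noncentrality is 200/72.5 = 2.76. Power is 78.4% (78.7% by normal approximation), or 79.2% for 202 g. The difference detectable with 80% power is about 204 g. This matches a rounded claim of 80% for about 200 g, so the formula is not in dispute.

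**2. The randomised contrast with its own SDs.** Pooled SD = √((588² + 603²)/2) = √((345,744 + 363,609)/2) = 595.5 g. The standard error is 78.5 g and the noncentrality is 200/78.5 = 2.55.

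| Contrast | SD (g) | Power for 200 g |
|---|---|---|
| Stated for any pair | 550 | 78.4% |
| Incentives vs best practices | 595.5 | 71.8% |
| Incentives vs nonsmokers | √((588² + 404²)/2) = 504.5 | 84.9% |
| Best practices vs nonsmokers | √((603² + 404²)/2) = 513.2 | 83.7% |

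For the randomised contrast, power at 202 g is 72.6%, and 80% is reached at 221 g. Using the smaller SD, 588, in both arms still gives only 72.9%.

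**3. Effect of covariance adjustment.** Residual SD = 595.5 × √(1 − R²), 200 g:

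| Assumed R² | Residual SD (g) | Power |
|---|---|---|
| 5% | 580.5 | 74.0% |
| 10% | 565.0 | 76.2% |
| 15% | 549.1 | 78.5% |

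Reducing 595.5 to 550 needs R² = 1 − 550²/595.5² = 14.7%. Power of 80% needs 18.1% for 200 g, or 16.4% for 202 g.

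**4. One error term for all three conditions.** √((588² + 603² + 404²)/3) = 539.3 g, for which the power formula gives 80.0%. That formula treats 539.3 as the true SD of the two randomised arms, which it is not. Simulating the three-condition model with SDs of 588, 603 and 404 (200,000 runs) gives 77.8% rejection of the randomised contrast at 200 g, but 7.6% when there is no difference. The two-group t-test in the same runs gives 71.8% and 5.1%.

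**5. Losses.** The analysis set is intention-to-treat "with the exception of excluding women for abortion/fetal demise as is convention in this research area". No rate is given. If 5% or 10% of each arm were lost, unadjusted power would be about 69.5% or 67.2%.

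**The case against.** The strongest reply is that 72% describes a test the plan does not use. The plan specifies covariance analysis on known predictors of birth weight, and an R-squared of about 15% would make 550 a fair residual SD. That may be so, and it is why the 72% is labelled unadjusted. But the plan calls 550 pooled, sets it beside raw group SDs and states no R-squared, so a reader cannot take it as adjusted.

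A second reply is that 550 was meant for all three conditions and is slightly conservative against their pool of 539. That origin is an inference. Even if it is correct, the pool is lowered by nonsmokers who are not part of the randomised contrast, and the apparent gain in power comes with a type I error above 5%.

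Third, 588 and 603 are themselves estimates, and the plan does not give the sample sizes behind them, so a true SD of 550 cannot be excluded. That is fair, but the plan offers these SDs as support for its claim, and they do not support it.

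Fourth, larger vouchers for heavier smokers are expected to widen the abstinence gap from 27 points (34% vs 7%) to about 40 (50% vs 10%). If birth weight scaled in proportion, the effect would be 202 × 40/27 = 299 g, with about 97% power even at SD 595.5. The plan makes no such projection, and it would not alter the power at the 200 g it states.

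Finally, the Economic Evaluation describes the outcomes "with antepartum abstinence being primary", so the main result is not at risk. That stands and limits the weight of the point.

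**Conclusion.** The concern holds. The arithmetic at SD 550 is sound. The fault is that 550 is applied to a contrast whose two quoted SDs are both larger. With those SDs, 115 per arm and no adjustment, the randomised comparison has about 72% power for 200 g, some 8 points below the stated 80%, and reaches 80% at about 221 g. Adjustment with an assumed R-squared of 5% to 15% gives 74% to 78.5%, and about 18% is needed for 80%. These figures take the prior-trial SDs at face value and assume no loss of birth-weight data. The finding is confined to birth weight; the abstinence and breastfeeding power statements stand.

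**What to change.** Either of two changes to the Sample Size Justification would settle this.

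- Restate the birth-weight power for incentives vs best practices with an SD of about 595: roughly 72% for 200 g, or 80% for about 221 g, unadjusted. In that case, confine the 80% claim for 200 g to the contrasts with nonsmokers.
- Or keep 550, state that it is the residual SD after adjustment for BMI, parity and sex, and give the assumed R-squared (about 15%) with its source. The claim for all pairs can then stay, with power for the randomised contrast given as about 78% for 200 g, or 80% for about 204 g.

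Under either option, say how 550 was obtained, and note that exclusions for abortion or fetal demise would lower power further. The cost is wording only; under the first option the stated power becomes less favourable. No extra enrolment and no change to the planned analysis is needed.

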### **Economic Evaluation**

**Cost analysis.** We will conduct an economic evaluation from the societal perspective including both cost-effectiveness and cost-benefit analyses (Drummond et al., 2005). The outcome measures in this trial were described above, with antepartum abstinence being primary and the related outcomes of longer-term abstinence, birth outcomes, and health and health care utilization in the 1st year postpartum important as well. Each of these outcomes can be viewed from the perspective of incremental cost effectiveness (e.g., the incremental cost to produce an additional abstinent mother at final antepartum assessment). We hypothesize that the best practices plus incentives intervention will be cost-effective (i.e., dominant) as compared to the best practices alone condition. To determine the cost of each intervention, we will employ the Brief Drug Abuse Treatment Cost Analysis Program (Brief DATCAP; French et al., 2004; French, 2010), which has been widely used in the area of

substance abuse, including projects utilizing incentives (Knealing et al., 2008). The direct and indirect economic cost of treatment will be derived by allocating fixed costs based upon the proportion of time or space utilized by the programs (e.g., treatment facility costs), as well as costs that vary by patient engagement and smoking status (e.g., drug tests, quitline staff time, incentives). The total cost per treatment episode will be individual specific and will include the opportunity cost of the patient's time while in treatment (Salomé et al., 2003; French 2005). The time period of the cost analysis will span from intake to discontinuation or completion of the program. However, since the duration of treatment will vary according to where in the pregnancy a woman enters the study, the economic cost per person per week will also be calculated. The cost of all research-specific resources consumed will be excluded from the evaluation. All costs and benefits will be expressed in a common dollar year without the need for discounting. Estimated treatment costs will be combined with the maternal and infant health outcomes outlined above to conduct the economic evaluation. Cost-effectiveness analysis (CEA). CEA will be conducted wherein the average (mean) difference in treatment costs across the two interventions will be divided by the average (mean) difference in each outcome to derive incremental cost-effectiveness ratios (ICERs). Statistical significance of these ICERs will be determined probabilistically by employing nonparametric bootstrapped standard errors (Drummond et al. 2005). Priority will be given to comparing ratios on key birth outcome measures and NICU admissions. Additionally, a special form of CEA, cost-utility analysis (CUA), will be performed. Based upon smoking status from the quit date through one year postpartum, the number of quality-adjusted life years (QALYs) gained by the mother—as measured by the proportion of time spent in ‘smoking’ and/or ‘nonsmoking’ status—will be derived using QALY weights recommended in the extant literature (e.g., Cromwell et al., 1997; Flack et al., 2007). Women still abstinent at 1 year postpartum will be treated as long-term quitters. QALYs gained by the infant will be calculated using QALY weights recommended in the literature (Taylor et al., 2009). The incremental cost per QALY gained

between the two modalities will be calculated and compared for mothers and infants separately and also summed across mother-infant dyads.

**Cost-benefit analysis (CBA).** CBA can often be especially useful by allowing consideration of multiple, often very different, outcomes. CBA yields two specific evaluation metrics, which are both placed in monetary terms, the benefit-cost ratio and the net benefit, that can be compared across health programs and economic sectors. We will conduct a partial CBA from a societal perspective for the intake through 12month postpartum period. Total health care costs for the mother and infant will be measured using the ‘allowed’ amounts extracted from administrative insurance claims data collected from health care providers. Adding smoking cessation treatment costs to health care costs will yield the total economic cost of care for a mother/infant dyad for the specified time period. Given randomization, the mean difference across the treatment arms (the average net benefit) will be attributed to intervention effectiveness. Cost benefit ratios also will be calculated and compared across the two treatment conditions for statistically significant differences. Sensitivity analysis. A multiway sensitivity analysis will assess the levels to which our incremental cost effectiveness ratios (ICERs) are robust to changes in component assumptions and costs. For example, while a theoretical 100% quit rate may never reach the low cost of treating the group of nonsmokers in our third condition, we can explore the maximum threshold of incentive required to maximize health benefits with respect to their costs one year postpartum. More within a realistic target, a 50% quit rate, for example, may be cost effective under all exploratory ranges of incentive compensation. The sensitivity analysis will therefore explore changes to assumptions over a broad range.

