hypothetical monetary rewards (Johnson & Bickel, 2002). Appropriately modified versions of this battery will be completed again at the second prenatal care visit and 28-weeks gestation, and then 2-, 4-, 8-, 12-, 24-, and 48-weeks postpartum. We will also assess breastfeeding, including initiation, duration, and different levels of breastfeeding (e.g., exclusive, predominate, any). All women will complete the Postpartum Bonding Questionnaire to examine associations between breastfeeding and maternal/infant bonding (Brockington et al., 2001). Breastfeeding is associated with significant improvements in a wide range of maternal and infant health outcomes, but there have been few opportunities to examine experimentally altered rates of breastfeeding due to the absence of ethical methods to manipulate them (Ip et al., 2007). The proposed study may provide an opportunity to do so by altering smoking status, which in turn impacts breastfeeding duration (Higgins et al., 2010b). These assessments will be conducted with all subjects independent of smoking status or treatment condition. Women will receive \$50 per assessment independent of smoking status. We also plan to assess health outcomes and health care utilization for use in the cost-effectiveness analysis. Permission will be requested of all women to review maternal and infant health care records through one-year postpartum and to telephone mothers monthly during postpartum to review infant health and health care visits. Project staff will review records by obtaining faxed copies or visiting the offices of local providers/pharmacies at the time of each of the regularly scheduled assessments. We will track the incidence of smoking-related pregnancy complications, delivery complications, and maternal and infant health outcomes during the 1st year postpartum (all illnesses requiring a visit to a healthcare professional). Infant outcomes will include birth outcomes (mean birth weight, % low birth weight deliveries (< 2500 g), mean gestational length, % premature deliveries (< 37 weeks), incidence of NICU admissions and mean length of stay, and health outcomes through one year postpartum (respiratory distress syndrome, upper and lower respiratory infections, otitis media, sudden infant death syndrome, and other infant death). We will track all maternal prenatal and postpartum health care utilization including pharmacy use through one-year postpartum and infant utilization through one-

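### The cost-effectiveness ratios count treatment cost only, so they cannot show the dominance that the plan hypothesizes under a societal perspective

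*Combined protocol and SAP*

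**What the plan says.** All of the following are in Economic Evaluation unless another section is named.

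- **Perspective:** "We will conduct an economic evaluation from the societal perspective including both cost-effectiveness and cost-benefit analyses".
- **Hypothesis:** "We hypothesize that the best practices plus incentives intervention will be cost-effective (i.e., dominant) as compared to the best practices alone condition".
- **Cost window:** "The time period of the cost analysis will span from intake to discontinuation or completion of the program". Under Treatment Conditions, vouchers stop at 12 weeks postpartum.
- **What enters:** "Estimated treatment costs will be combined with the maternal and infant health outcomes outlined above to conduct the economic evaluation". Treatment cost covers staff, tests, incentives and the woman's own time: "The total cost per treatment episode will be individual specific and will include the opportunity cost".
- **Ratio:** "the average (mean) difference in treatment costs across the two interventions will be divided by the average (mean) difference in each outcome". Priority goes to birth outcomes and NICU admissions.
- **Inference:** "Statistical significance of these ICERs will be determined probabilistically by employing nonparametric bootstrapped standard errors".
- **Cost-utility analysis (CUA):** described as a special form of the cost-effectiveness analysis (CEA). It reports an incremental cost per QALY and does not define the cost separately.
- **Cost-benefit analysis (CBA):** adds maternal and infant health care cost to treatment cost, from intake through 12 months postpartum, and compares the arms on the total.

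The Assessments section says: "We also plan to assess health outcomes and health care utilization for use in the cost-effectiveness analysis". The September 2021 entry in the History of Modifications adds a provider and/or public payer perspective, with reference to costs of adoption, and a new QALY method. It does not restate the ICER numerator.

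**The concern.** Dominance is a statement about two differences: lower cost and better effect. From a societal perspective, the cost side must include the health care that the intervention is expected to save. The ICER numerator as written leaves that out and stops counting at the end of the program. The hypothesis and the ratio offered to examine it therefore do not match.

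Cost-effectiveness is a headline aim of the trial. Followed literally, every ICER would price incentives as a pure extra cost, although the data that could offset that cost are collected and used elsewhere in the same evaluation.

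A secondary matter is how ICER significance is judged. A standard error of a ratio is unreliable when the denominator can come close to zero, and the outcomes given priority have weaker denominators than abstinence.

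**Working it through.** **1. The plan's own figures.** Antepartum vouchers: 5 tests in week 1, 14 at twice weekly for 7 weeks, 4 weekly and 10 fortnightly make 33 tests. Values rise from 5 points to the 36-point ceiling at $1.25 per point, which gives $865. Postpartum: 8 × $45 = $360. The total is $1,225, and half of it is $612.50, which matches the projected $613. Birth weight power (200 g, SD 550, 115 per arm) comes out at 78.7%, against the stated 80%. No stated figure is in dispute.

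**2. Sign of the numerator.** Best practices is common to both arms. The incentives arm adds vouchers averaging $613 (lower schedule) or $1,226 (higher schedule), plus staff, tests and patient time. Could lower quitline use offset this? In the extreme case, every control woman takes all 10 calls of about 10 minutes and no incentives woman takes any. Quitline time would then have to cost 613 / (10 × 10) = $6.13 per minute, or $368 per hour. The numerator is positive in practice.

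**3. What total cost could change.** The documents give no health care costs, so a corrected ICER cannot be computed. The break-even saving per NICU admission avoided is voucher cost divided by risk reduction, both for vouchers alone. At an assumed 5-point reduction:
- 613 / 0.05 = $12,260
- 1,226 / 0.05 = $24,520

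Over assumed reductions of 10 down to 2.5 points, the range is 613 / 0.10 = $6,130 to 1,226 / 0.025 = $49,040. With total cost the sign is an open question. With treatment cost it is not.

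**4. Standard error of the ratio, birth weight.** SE of the difference = 550 × √(2/115) = 72.5 g, and z = 200 / 72.5 = 2.76. By normal approximation, the 95% interval for the difference includes zero in 21% of trials. A nonparametric bootstrap used assumed treatment costs (mean $1,500, SD $700 vs mean $300, SD $150), a 200 g difference and 5,000 replicates. The ICER is 1,200 / 200 = $6 per g. Over 12 seeds:
- The SE of the ratio ran from $15 to $220 per g.
- Removing the 5 most extreme of the 5,000 replicates cut it to $6 to $14.
- Percentile limits were stable, at $3.4–3.5 and $18.6–21.9.

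**5. NICU admissions.** The documents give no rates, so these are assumed. The exact binomial probability of a zero or negative denominator with 115 per arm is:

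| Assumed rates | Probability |
|---|---|
| 20% vs 10% | 2.0% |
| 15% vs 10% | 14.6% |
| 10% vs 7.5% | 28.9% |

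In those replicates the ratio has no clear meaning.

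**6. Abstinence, 50% vs 10%.** SE of the difference = √((0.25 + 0.09) / 115) = 0.054, and z = 0.40 / 0.0544 = 7.4. The bootstrap SE was $455 to $475 on an ICER of 1,200 / 0.40 = $3,000, and no replicate had a denominator at or below zero.

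**The case against.** **The CBA already covers health care cost.** This is the strongest reply, and part of it stands. A reader might infer that the evaluation ignores health care savings, but it does not. The CBA compares total dyad cost between arms through 12 months, and that difference can be set beside the effect differences. The plan never makes that link, however, and its ICERs are explicitly built on something else.

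**Collecting utilization for the CEA proves a contradiction.** It does not. The plan also lists first-year utilization among its outcomes, so utilization could serve as a denominator. The sensitivity analysis also mentions the low cost of treating nonsmokers, who receive no cessation treatment. That remark is an illustration, not a specification. Both support a wider cost measure without being decisive.

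**The 2021 modification settles it.** Its reference to costs of adoption supports reporting a treatment-cost ICER, so that ratio is legitimate in itself. But the entry neither withdraws the societal perspective nor redefines the numerator, and a public payer perspective would also need health care cost.

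**The CUA's cost is unknowable.** That goes too far. As a special form of the CEA, it most naturally inherits treatment cost.

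**The bootstrap point depends on a reading.** This stands. The plan does not expressly say that the standard error is that of the ratio, and percentile limits for birth weight are stable. Nor should a reader infer that all ICERs are affected: abstinence is not. For NICU admissions the SE itself was stable across seeds, and the difficulty there is the sign of the denominator.

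**Conclusion.** The main point holds on the text and needs no simulation. The ICERs as defined cannot show the dominance that the plan hypothesizes, because their numerator is an add-on cost that is positive in practice. It should be fixed. It does not touch the abstinence comparison, and it is a defect of the ICERs and probably the CUA, not of the whole economic evaluation.

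The bootstrap point is secondary and conditional on reading the plan's standard error as that of the ratio. On that reading it holds for birth weight at the plan's own effect, SD and sample size, although the dollar figures rest on assumed costs. The NICU range of roughly 2% to 29% rests wholly on assumed rates.

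**What to change.** **(a) Numerator.** For the societal ICERs and the CUA, use the difference in total dyad cost that the CBA already computes (treatment plus maternal and infant health care through 12 months). State that the sensitivity analysis uses the same cost, and list what is counted, since the plan calls its CBA partial. Report the present ratio separately as a treatment-cost ICER. Do not label it provider-perspective while it includes patient time. For cost per NICU admission avoided, note that NICU savings then also enter the numerator. Record all this alongside the 2021 modification.

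**(b) Inference.** Report the bootstrap joint distribution of cost and effect differences, including the share of replicates that are cheaper and better. Add net monetary benefit with percentile intervals over a range of stated willingness-to-pay values. The documents give none, so they must be chosen and justified.

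**Cost.** The change needs analysis-plan wording and modest extra analysis of data already planned. The real price is precision:
- At assumed dyad-cost SDs of $10,000 and $40,000, the SE of the cost difference is 10,000 × √(2/115) = $1,319 and 40,000 × √(2/115) = $5,275.
- For birth weight at an assumed $10 per g, with cost and effect taken as independent, the SE of net benefit is √(725² + 67²) ≈ $730 with treatment cost, where 67 = √((700² + 150²) / 115). It becomes √(725² + 1,319²) ≈ $1,500 to √(725² + 5,275²) ≈ $5,300 with total cost.
- At an assumed true saving of $1,000 per dyad, about 77% down to 57% of replicates would be cheaper with higher birth weight.

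Dominance would therefore be reported as a probability with wide uncertainty.
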